1. Disease-specific health-related quality of life will be measured with the St. George's Respiratory Questionnaire; 76 items, 3 subscales (symptoms, activity, and impacts), each with score 0-100. The minimum clinically important difference is 4; 8 units reflect moderate change; and 12 units very efficacious treatment.
2. Combined # of COPD- related ED and hospital visits per patient from enrollment to 3, 6, and 9 months (also calculated separately for hospital and for ED visits).
3. Patient activation measure Pam -13 item. This instrument has been widely tested with patients with various medical conditions. It has been psychometrically tested and used in multiple research studies. The 13-item measure has similar psychometric properties to the original 22-item version which shows good precision and validity.
4. Understanding COPD questionnaire: Will use the sections on 'understanding of COPD' and 'self-efficacy and use of key self-management skills'. Good test-retest reliability (ICC range: 0.87 to 0.96) and internal consistency (Cronbach's Alpha range: 0.78 to 0.95). The instrument has been shown to be responsive to in studies of pulmonary rehabilitation. We will also use an adapted version of this questionnaire to measure self-efficacy among caregivers.
5. Medication adherence – Morisky scale. This is an 8-item scale that has been validated and used in multiple studies. The instrument was initially tested with hypertension patients but has since been used with different patient populations.
6. Social and other support- The Patient-Reported Outcomes Measurement Information System (PROMIS) item bank - four validated domains will be used: Social isolation; Informational support; Emotional support. .
7. Ways of Coping Questionnaire. Validated questionnaire with reliability of .76 - .88 and established construct validity.

Caregiver outcomes include self-efficacy, stress and coping, informational and emotional support, and experience with the intervention.

Please refer to 'Study Outcomes Table' attachment for full list of Patient and Caregiver outcomes and time points of data collection.

Data collection and outcomes assessment

It is not possible to 'blind' the patients, their families, or the healthcare professionals to the study assignment in this type of intervention. However, we will have the study research coordinators and any other personnel who are involved in outcome assessment blinded to the study participants' arm assignment.

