Home oxygen use	✓		✓	✓	No oxygen/oxygen continuously/oxygen with activity and/or sleep
Depression treatment	✓				One item on receiving treatment for depression: currently/during past 2 years/never
Health status	✓	✓	✓	✓	Patient self-report
Functional status	✓		✓	✓	Katz Index of Independence in Daily Living
Patient anxiety and depression	✓		✓		PROMIS anxiety (8 questions) and depression (4 questions) measures Response options: Never/rarely/sometimes/often/always
Cognitive status	✓				Minicog

Patient participation in study interventions			✓	HCP and Peer support program participation Participation in other programs
Co-morbidities	✓	✓		Charleson co-morbidity index based on coded diagnosis from medical record at baseline Patient self-report at 6 months on new heart conditions or cancer
Major life events		✓		Loss of caregiver, change in living status, new health conditions or terminal diagnosis, other
Patient Activation	✓	✓	✓	Patient Activation Measure (PAM 13)
Self-efficacy	✓	✓	✓	Understanding COPD Questionnaire- Select questions)
Self- care behaviors: Physical activity, smoking status, etc.	✓	✓	✓	Select questions from Understanding COPD questionnaire, change in smoking status, physical activity
Medication Adherence	✓		✓	Morisky Medication Adherence Scale (4 items)
Patient perceptions of caregiving	✓		✓	Perceptions of caregivers' support and their preparedness to assist with COPD management; caregiving activities received
PROMIS support measures	✓	✓	✓	PROMIS item bank- 4 domains will be used (each domain has 4 items): 1) Social isolation; 2) Informational support; 3) Emotional support; 4) Instrumental support. There are 5 response options: Never/rarely/sometimes/usually/always
Hope	✓	✓	✓	Herth Hope index (12 item instrument) with 3 subscales
Participation in pulmonary rehabilitation	✓	✓	✓	Percentage of patients enrolled in pulmonary rehabilitation; Mean number of sessions attended per week
Post hospitalization ED visits and readmissions (COPD - related and all cause)	✓	✓	✓	Measure: Average number of visits per patient in the 6 months post enrollment (calculated as Combined ED and hospitalizations; ED only; Hosp. only). Based on patient self-report (Y/N ; circumstances/reasons for seeking these services) followed by medical records confirmation
COPD - specific quality of life : Total score; domain scores	✓		✓	St. George's Respiratory Questionnaire (SGRQ)

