Hypothesis: Patients receiving the HCP PLUS Peer Support will have a lower rate of hospitalizations and ED visits than patients in the *HCP only* group.

4. Total combined number of *all cause* hospitalizations and ED visits at 3, 6, and 9 months post-enrollment.

Hypothesis: Patients receiving the HCP PLUS Peer Support will have a lower total number of *all cause* hospitalizations and ED visits than patients in the *HCP only* group.

5. Change in HRQOL based on SGRQ domain scores at 3, 6, and 9 months post-enrollment.

Hypothesis: Patients receiving the HCP PLUS Peer Support will have larger improvement in HRQOL (larger negative change in SGRQ score) compared to baseline, than patients in the *HCP only* group.

6. Mortality rate at 3, 6, and 9 months post-enrollment.

Hypothesis: Patients receiving the HCP PLUS Peer Support will have a lower mortality rate compared to patients in the *HCP only* group.

Intermediate Measures:

7. Change in PROMIS support domain scores (Instrumental, Informational, Depression, Anxiety, Social Isolation, and Emotional Support) at 3, 6, and 9 months post-enrollment.

Hypothesis: Patients receiving the HCP PLUS Peer Support will have larger positive change in PROMIS scores compared to baseline, than patients in the *HCP only* group.

8. Change in Herth Hope Index total score at 3, 6, and 9 months post-enrollment.

Hypothesis: Patients receiving the HCP PLUS Peer Support will have larger positive change in Hearth Hope Index scores compared to baseline, than patients in the *HCP only* group.

9. Change in Patient Activation Measure (PAM) scores at 3, 6, and 9 months post-enrollment.

Hypothesis: Patients receiving the HCP PLUS Peer Support will have larger positive change in PAM scores compared to baseline, than patients in the *HCP only* group.

10. Change in patient's understanding and self-efficacy, as measured by the *Understanding COPD questionnaire's* three components (About COPD, Symptom Management, and Accessing Help and Support) at 3, 6, and 9 months post-enrollment.

Hypothesis: Patients receiving the HCP PLUS Peer Support will have larger positive change in understanding and self-efficacy levels compared to baseline, than patients in the *HCP only* group.

11. Morisky adherence levels at 6 months post-enrollment.

Hypothesis: Patients receiving the HCP PLUS Peer Support will have a higher level of adherence compared to patients in the *HCP only* group.

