12. Participation in pulmonary rehabilitation at 3, 6, and 9 months post-enrollment.

Hypothesis: Patients receiving the HCP PLUS Peer Support will have greater level of participation in pulmonary rehabilitation than patients in the *HCP only* group.

13. Change in smoking status at 3, 6, and 9 months post-enrollment.

Hypothesis: Patients receiving the HCP PLUS Peer Support will have a higher smoking cessation rate than patients in the *HCP only* group.

Handling of Missing Data (PCORI [name]-4)

There are two types of missing data, at the respondent level (unit non-response) and at the specific question level (item non-response). At the respondent level, missing data occurred because of patient death, withdrawal from study, or inability to be reached via phone for an interview. Comparisons of missingness by several patient characteristics at baseline will be performed with Fisher's exact or Chi-Square tests to examine any potential systematic pattern to the missing data. For the specific case of the SGRQ instrument, values of 100 (the worst possible QoL score) will be imputed for any assessment in which a patient was not available because of death.

With respect to data at the specific question level, missing data will be handled according to each instrument collection manual. In some cases, for example the SGRQ,¹ PAM,² and PROMIS-anxiety,³ -depression,⁴ -emotional,⁵ and -instrumental support index⁶ score will be prepared in instrument specific calculators, provided by the instrument's authors, and accounted for any assignments of missing scores based on the availability of item responses. Missing data for other instruments such as PROMIS-social isolation⁷ and -informational support index⁸, understanding COPD⁹, and Morisky measure,¹⁰ will be handled according to the instrument's author's direction.

When no information is available for handling missing item responses on a particular instrument, a rule, allowing no more than 25% of the items for the scale/domain to be missing, was used. If less than 25% of the item responses were missing, the mean of the non-missing item responses

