The primary repeated outcome (SGRQ) will be evaluated using a linear mixed RE model. Within this model, the primary hypothesis about change in HRQOL from baseline to 6 months, will be evaluated by a hypothesis test of the interaction term between study group and the 6-month time variable.

For secondary outcomes, we will fit appropriate generalized linear mixed RE models based on the type of outcome variable. Continuous measures, such as for HERTH Hope Index or PROMIS support domain scores, will be assessed using linear mixed RE models. Binary outcomes, such as Morisky adherence to medication, will be assessed using logistic mixed RE models. Outcomes that are cumulative counts, such as number of hospitalizations and ED visits, will be assessed using Poisson or negative binomial mixed RE models, as appropriate. Differences in change in outcome from baseline to 3, 6, and 9-months between the study groups will be assessed by including interaction terms between the time variables and study group. We will assess significance by first testing the overall interaction between time and group. If the overall interaction is significant for an outcome measure, we will then estimate and test individual time differences accounting for multiple testing using a Bonferroni correction. Initially models will be adjusted only for baseline measure, site, and recruitment setting. We will also consider adjusting for patient characteristics such as age, gender, presence of caregiver, home oxygen use, and prior hospitalization.

Unadjusted survival analyses using Kaplan-Meier and log rank tests will be performed for *time to death or first COPD-related hospitalization or ED visit*. Statistical significance will be considered for $p < 0.05$.

Complier-Average Causal Effect (CACE) using Instrumental Variable Estimation

CACE: Primary Outcome

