gender, disease severity (whether they are on continuous home oxygen), baseline PAM score (collapsed into low vs high levels), and caregiver presence (caregiver vs no caregiver). Within the HCP PLUS Peer Support group, we will also consider subgrouping by the propensity for adherence to treatment (collapsed into low vs high levels), with propensity for adherence to treatment as the estimated probability of adherence to treatment from our intervention implementation analysis described above.

HT-2, HT-3:

Subgroup treatment effects will be estimated by including a three-way interaction between the subgroup variable, the study assignment variable, and the 6-month time variable in a generalized linear mixed RE model. We will test for a difference in treatment effect between subgroups by a hypothesis test of the overall three-way interaction in this model. We will report estimates of subgroup treatment effects with corresponding 95% confidence intervals (CIs). For the comparison of propensity for adherence groups within the HCP PLUS Peer Support group, we will include an interaction between the subgroup variable and the 6-month time variable, test this interaction, and estimate subgroup effects with corresponding 95% CIs.

References

1. Jones PW. St George's Respiratory Questionnaire Manual. 2009;44(June):0-16.
3. PROMIS. Anxiety. A brief guide to the PROMIS Anxiety instruments. 2018:1-18.
4. PROMIS. Depression. A brief guide to the PROMIS Depression instruments. 2018:1-18.
5. PROMIS. Emotional Support. A brief guide to the PROMIS Emotional Support instruments. 2017:1-6.
6. PROMIS. Instrumental Support. A brief guide to the PROMIS Instrumental Support instruments. 2017:1-6.
7. PROMIS. Social Isolation. A brief guide to the PROMIS Social Isolation instruments.

2015:1-7.

8. PROMIS. Informational Support. A brief guide to the PROMIS Informational Support v2.0 instruments. 2015:1-7.

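### The Morisky medication-adherence measure is given as both 8 and 4 items and is analysed as yes/no with no scoring rule or cut-off; a full-score analysis would be a cheap improvement

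*Combined protocol and SAP*

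**What the plan says.** **Instrument.** Protocol section 4, Study Measures and Outcomes, item 5, says of the Morisky scale: "This is an 8-item scale that has been validated and used in multiple studies". The outcome table in protocol section 7.b lists the "Morisky Medication Adherence Scale (4 items"). The SAP gives no item count. Its only source for the instrument is reference 10, which appears as a citation titled "Concurrent and Predictive Validity of a Self-Reported Measure of Medication Adherence".

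**Outcome.** SAP Intermediate Measures, item 11, is "Morisky adherence levels at 6 months post-enrollment". The hypothesis is that patients in the combined arm "will have a higher level of adherence compared to patients in the" HCP-only group. No threshold is named.

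**Analysis.** SAP Statistical Analysis: "Binary outcomes, such as Morisky adherence to medication, will be assessed using logistic mixed RE models". The same paragraph treats other multi-item scores differently: "Continuous measures, such as for HERTH Hope Index or PROMIS support domain scores, will be assessed using linear mixed RE models". All these models adjust for the baseline measure, site and recruitment setting. The same section also plans exploratory summaries of each outcome across the two study groups, to assess distributions and missingness.

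**Missing items.** For the Morisky measure and some others, these "will be handled according to the instrument's author's direction". That covers missing responses, not how a completed questionnaire becomes adherent or not adherent.

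**The concern.** Someone programming this analysis needs three things that the documents do not settle: how many items there are, how they are scored, and which scores count as adherent. A cut-off for one version need not carry over to the other, and the protocol's validity statement is attached to the 8-item version while its table lists 4 items. Two analysts could follow the SAP faithfully and build different response variables.

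The missing cut-off matters more because the SAP plans to inspect outcome distributions by study group. If the cut is still open at that point, it could be chosen with the arms in view.

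Separately, the SAP gives no reason for splitting this score in two while it analyses the Herth Hope Index and PROMIS scores in full. The score is collected at baseline as well as follow-up, so a full-score analysis needs no new data.

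**Working it through.** The documents give no rate, SD, power or sample size for this outcome, so there is no figure of the plan's own to reproduce. The first step is textual and the rest is illustrative.

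**1. Side by side.**

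| Place | Items | Scoring or cut-off |
|---|---|---|
| Protocol section 4, measures, item 5 | 8 | none |
| Protocol section 7.b, outcome table | 4 | none |
| SAP, Intermediate Measures, item 11 | not stated | none |
| SAP, Handling of Missing Data | not stated | missing items only |
| SAP, Statistical Analysis | not stated | binary, no cut-off |

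The SAP's rule of four or more encounters defines adherence to peer support, not to medication, so it does not fill the gap.

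**2. Information kept by a split, normal score (assumption).** Efficiency relative to the full score is φ(z_p)² / [p(1−p)], where p is the proportion classed adherent.

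- p = 0.50: 0.3989² / 0.25 = 0.64
- p = 0.40: 0.3863² / 0.24 = 0.62
- p = 0.30: 0.3477² / 0.21 = 0.58
- p = 0.20: 0.2800² / 0.16 = 0.49

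**3. The same loss as power.** Evaluable patients per arm: 145 × 0.85 = 123, from the stated sample size and attrition. The shift giving 80% power on the full score at two-sided 0.05 is (1.960 + 0.842) × √(2/123) = 0.357 SD. After a split, power is about 60% with 50% or 40% of controls adherent, 59% with 30%, and 53% with 20%. Restoring 80% would take 195 to 230 evaluable per arm.

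**4. Five-level score (assumption: shares 5/10/20/30/35%, proportional odds).** Efficiency of a split with proportion p on one side is 3p(1−p) / (1 − Σpᵢ³).

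- Σpᵢ³ = 0.000125 + 0.001 + 0.008 + 0.027 + 0.042875 = 0.079, so the denominator is 0.921
- Cut at 35% or 65%: 3 × 0.35 × 0.65 / 0.921 = 0.74
- Cut at 15%: 3 × 0.15 × 0.85 / 0.921 = 0.42
- Cut at 5%: 3 × 0.05 × 0.95 / 0.921 = 0.15

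**5. Sensitivity to the shape.** With shares 50/20/15/10/5% cut at 50%, Σpᵢ³ = 0.1375 and efficiency is 0.75 / 0.8625 = 0.87. For beta-binomial sum scores on 4 or 8 items, with 30 to 70% of patients on one side of the cut, efficiency against a comparison of means runs from about 0.60 to about 1.0. The top of that range occurs when many patients sit at the floor.

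**6. What an open cut could do.** In a simulation with no true effect, 123 per arm and assumed five-level distributions, one fixed cut gave about 5% false positives. Taking the best of four cuts gave 15 to 17%, and the better of the top two about 9%. This shows why the cut should be fixed. It is not evidence that anyone would choose it this way.

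**The case against.** The strongest reply is that this is one intermediate measure, item 11 of 13 in the SAP's list, and that percent adherent is a legitimate and easily read summary. Once the version and one cut-off are written down, the binary analysis is properly pre-specified. That stands. A pre-specified split would be valid, and the case for the full score is one of efficiency and consistency.

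Several stronger readings are tempting but not supported:

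- **That 4 items is the right count because of the SAP's cited source.** The documents show only that source's citation, with no item count or scoring. They set one protocol passage against another and do not say which is correct.
- **That *levels* in item 11 contradicts a binary analysis.** The SAP's heterogeneity section also uses that word for low-versus-high groupings, so it is compatible with two categories.
- **That baseline adjustment is an advantage peculiar to the full score.** The SAP already adjusts every secondary model for baseline.
- **That the endpoint is wholly undefined, or that the cut will be picked after seeing data.** The instrument family, 6-month time point, direction and model class are all stated. Only the version, scoring and threshold are missing, and a late choice is a possibility, not a fact.

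**Conclusion.** The point holds as a low-severity improvement. The 8-versus-4 conflict and the absence of a scoring rule or cut-off are established by reading and need no assumption. Full-score analysis is the better main analysis for a score already collected, and it matches the SAP's handling of its other scales.

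The size of the gain cannot be stated for this trial. A reader might turn the 0.74 into a loss of about 64 patients (0.26 × 246, with 290 × 0.85 = 246). That number rests on assumed shares: 0.87 efficiency would give about 32 (0.13 × 246), and clustering at one end could make the loss close to nil. The five-level figures also assume 4 items scored 0 to 4 and proportional odds, neither of which the documents state.

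Nothing here touches the SGRQ comparison or the 145 per arm.

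**What to change.** 1. State once, in the protocol and the SAP, which Morisky version was administered, with its item count and scoring, and reconcile protocol section 4 item 5 with the section 7.b table. The count also matters for missing data. If the author's guidance were silent and the SAP's default rule applied, one missing item of four is exactly 25%, which that rule leaves unassigned.
2. Make the main analysis the full 6-month score, by proportional-odds or linear model, adjusted for baseline score, site and recruitment setting. Because item 11 names only 6 months, say that the overall time-by-group test across 3, 6 and 9 months does not apply to this outcome.
3. Keep percent adherent by arm as a supportive summary, at one cut-off with its source, fixed before any unblinded analysis, including the exploratory summaries by study group.

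The cost is wording only, with no new data. The downside is that a common odds ratio or mean difference is slightly less intuitive than a percentage adherent, which the supportive summary still provides.

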All participants will be interviewed in person, upon enrollment, prior to randomization, by a trained study team member. At the enrollment visit, baseline data will be collected on demographics, bio-psychosocial status, as well as COPD knowledge, self-management skills, patient activation, and health literacy levels. Participants will then be interviewed via phone by a research team member, who is blinded to their study group assignment at 3-, 6-, and 9-months post enrollment. Similarly, we will collect data from caregiver participants who will be surveyed upon enrollment, and at 3-, 6-, and 9-months follow up post enrollment. Due to the study end date, it will not be possible to collect 9-month follow-up data for participants who enrolled later in the study.

Additionally, information will be collected post enrollment on whether the patient has visited the ED or been re-hospitalized via Chesapeake Regional Information System for our Patients (CRISP). CRISP will be used determine whether the visit was COPD-related using a set of pre-determined discharge diagnoses.

Study Outcomes and Hypotheses

The study groups will be compared for the following outcomes:

Primary Outcome for Patient Participants:

1. Change in health-related quality of life (HRQOL) as measured by the St. George Respiratory Questionnaire (SGRQ) total score, from baseline to 6 months post-enrollment.

Hypothesis: Patients in the HCP PLUS Peer Support group will have a larger improvement in HRQOL (larger negative change in SGRQ score) at 6 months post discharge compared to baseline, than patients in the *HCP only* group.

Secondary Outcomes and Intermediate Measures for Patient Participants:

Secondary Outcomes:

1. Change in HRQOL based on SGRQ total score at 9 months post enrollment.

Hypothesis: Patients in the HCP PLUS Peer Support group will have larger improvement in HRQOL (larger negative change in SGRQ score) compared to baseline, than patients in the *HCP only* group.

2. Total number of COPD-related hospitalizations and ED visits at 3, 6, and 9 months post-enrollment.

Hypothesis: Patients receiving the HCP PLUS Peer Support will have a lower rate of COPD-related hospitalizations and ED visits than patients in the *HCP only* group.

3. Total combined number of *all cause* hospitalizations and ED visits at 3, 6, and 9 months post-enrollment.

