was calculated and was used to replace the value of the missing item responses before calculation of the scale/domain score. This approach weights the scale/domain score towards the respondent's mean response and is balanced by requiring a large majority of item responses to be available. If more than 25% of the item responses were missing, the scale/domain score was considered missing.

Statistical Analysis (PCORI Standard IR-1, RC-4)

Statistical summaries and distributions of patient characteristics will be reviewed by study site (JHBMC and HCGH) and by recruitment setting (inpatient and outpatient). Statistical summaries and distributions of patient and clinical characteristics will also be reviewed across study groups. Randomization of the patients to the study groups expects that on average the groups were balanced on characteristics that might affect the study results, such as socio-demographic and health status. Thus, no statistical tests to compare the groups on patient characteristics will be performed.¹¹

Exploratory analyses will be performed cross-sectionally at baseline, 3, 6, and 9 months post-discharge for each of the outcomes across the two study groups. This will provide an assessment of the outcomes' distributions, missingness patterns and the need for additional data review and quality assurance.

The main analysis approach for assessing the change in the primary outcome measure from baseline, as well as changes in secondary outcome measures from baseline, will consist of performing analyses of the treatment effect between the two study groups under intention to treat (ITT) adjusted for baseline measure, site, and recruitment setting.

Repeated outcomes in this study will be evaluated using generalized linear mixed random-effects (RE) models. The generalized linear mixed RE model reflects the study's interest in comparisons of change at the individual level, where the changes may be subject-specific and reflective of potentially unmeasured variables. This model also fits well with the approaches related to

missing data and heterogeneity of treatment effects discussed below. In particular, this approach will help us handle the missing 9-month data for participants who enrolled later in the study.

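### Hospital and ED visit totals at 3, 6 and 9 months overlap, so on the plain reading the mixed count model's overall time-by-group test is too conservative

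*Combined protocol and SAP*

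**What the plan says.** Four statements together fix the analysis of visits.

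- **Windows.** Protocol, Study Measures and Outcomes, item 2, counts "ED and hospital visits per patient from enrollment to 3, 6, and 9 months". SAP secondary outcome 2 is "Total number of COPD-related hospitalizations and ED visits at 3, 6, and 9 months post-enrollment". Outcomes 3 and 4 use the same time points for all-cause visits.
- **Model family.** SAP, Statistical Analysis: "Repeated outcomes in this study will be evaluated using generalized linear mixed random-effects (RE) models". For visits in particular: "Outcomes that are cumulative counts, such as number of hospitalizations and ED visits, will be assessed using Poisson or negative binomial mixed RE models".
- **Contrast.** "Differences in change in outcome from baseline to 3, 6, and 9-months between the study groups will be assessed by including interaction terms" between time and group.
- **Order of testing.** "We will assess significance by first testing the overall interaction between time and group". Individual time points are estimated and tested, with a Bonferroni correction, only if that overall test is significant.

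Neither document converts the totals to interval counts, names an exposure offset, gives a covariance for nested totals or asks for robust standard errors. The hypotheses for outcomes 2 and 3 speak of a rate, and the one for outcome 4 says patients "will have a lower total number of" visits. No person-time term appears for any of them.

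**The concern.** A time-by-group term needs one row per patient per time point. If those rows hold totals from enrollment, a visit in month 2 appears in all three rows. A Poisson or negative binomial mixed model treats a patient's rows as independent once the patient effect is given. Nested totals break that assumption: the 6-month row is the 3-month row plus whatever happened since. The random intercept captures that some patients have more visits than others. It does not capture that two rows contain the same events.

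The overall interaction test is the gate to every time-specific result from this model. The peer programme runs for 6 months, so a benefit that grows with exposure is a natural pattern to expect. It is also a pattern that this test needs correct between-time variances to see. Acute-care use is part of the stated research question, so a false finding of no difference here would matter.

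**Working it through.** **Inputs.** The documents give 290 enrolled and 1:1 allocation, hence 145 per arm. They give no visit rate, between-patient variance, power or error figure for the visit outcomes, so there is no planned figure to reproduce. (The planned 145 per arm was derived for the SGRQ.) Assumed here: m = 0.3 to 0.6 visits per patient per 3 months, complete follow-up, and a patient risk that is constant over time.

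**Counting.** Visits in months 0-3 enter three rows, those in months 3-6 two rows, and those in months 6-9 one row. At a constant rate the rows hold 3 + 2 + 1 = 6 units for every 3 real ones.

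**Variance, post-baseline rows only.** In a Poisson random-intercept model with complete rows, the patient effect cancels from the group-by-time test, which then depends on the arm totals. With n patients in an arm, the expected totals at 3, 6 and 9 months are nm, 2nm and 3nm.

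- 6 versus 3 months, rows taken as independent: 1/(2nm) + 1/(nm) = 1.5/(nm).
- The logs of the two totals have covariance nm/(nm × 2nm) = 1/(2nm). The true variance is 1.5/(nm) − 2 × 0.5/(nm) = 0.5/(nm).
- Ratio 3.0, so the SE is √3 = 1.73 times too large.
- 9 versus 3 months: the model uses 4/(3nm), the truth is 4/(3nm) − 2/(3nm) = 2/(3nm), ratio 2.0.

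Example with n = 145 and m = 0.3: nm = 43.5. For the between-arm contrast at 6 versus 3 months, the true variance is 2 × 0.5/43.5 = 0.0230 (SE 0.152). The model uses 2 × 1.5/43.5 = 0.0690 (SE 0.263).

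**Effect on the tests.** A nominal 5% test of the 6 versus 3 month contrast rejects only beyond 1.96 × 1.73 = 3.39 true SEs, a probability of 0.0007. For 9 versus 3 months the figure is 1.96 × 1.41 = 2.77, probability 0.0056. Simulation gave the same values.

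**Overall test, simulated, 145 per arm.** The building effect is a visit rate lower by 0%, 25% and 50% in the three successive intervals. The baseline row is a prior-year count set at 4 times the 3-month rate.

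| Layout | Setting | Cumulative rows | Interval rows |
|---|---|---|---|
| Post-baseline rows only | Null | under 0.1% | about 5% |
| Post-baseline rows only | Building effect, m = 0.3 | about 3% | about 44% |
| Post-baseline rows only | Building effect, m = 0.6 | about 13% | about 75% |
| With baseline row | Null | about 3% | about 5% |
| With baseline row | Building effect, m = 0.3 | about 20% | about 60% |
| With baseline row | Building effect, m = 0.6 | about 45% | about 90% |

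With the baseline row, each single contrast against baseline keeps its size (0.049-0.050), because those two windows do not overlap. The overall test is still off, because the model misses the covariance among the follow-up totals. Maximum-likelihood fits of the Poisson random-intercept model with post-baseline rows agreed: 0% null rejection with cumulative rows, and a model SE 1.66-1.69 times the true SD.

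**Limit of interval rows.** If a patient's risk also varies independently from interval to interval (gamma, shape 1-2), a plain Poisson random-intercept fit to interval rows rejects a true null in 11-29% of trials. The fix must allow for that variation.

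**The case against.** **The row layout is inferred.** Neither document writes out the data rows, and the protocol's outcome table also describes the measure as an average per patient over the 6 months after enrollment, which is a single window. That stands: a sentence specifying interval counts would remove the problem. But the SAP itself calls the counts cumulative, places repeated outcomes in mixed models and asks for time-by-group terms, and no other layout is written.

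**A baseline row may be intended.** The contrast is worded as change from baseline, which allows a baseline row. The same paragraph adjusts for the baseline measure, which points to post-baseline rows only. Both readings are open, and the loss is much milder with a baseline row. In that layout a steady rate ratio of 0.7 is not penalised at all: the overall test rejected in 43% of trials with cumulative rows and 37% with interval rows at m = 0.3.

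**The negative binomial option.** It should not repair the fault, because nested totals vary too little within a patient, not too much. This is reasoned, not simulated.

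**Stronger readings.** A reader might infer that counting visits up to three times creates false positives or biased estimates. Neither was shown. The overall test was conservative in every setting run, and point estimates at a given time are valid under the Poisson assumption. A reader might also infer that a growing benefit cannot be detected; power is low, not zero. Nor does the gate cover every analysis of visits: the CACE analyses and the log-rank test of death or first COPD-related visit are planned with no such gate.

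**Conclusion.** The point holds on the plain reading of the two documents. With post-baseline rows only, the overall time-by-group test for visits has a true size under 0.1% instead of 5%. It has about 3-13% power for a building benefit that interval counts would detect with 44-75% power. With a non-overlapping baseline row, the size is about 3%, the power about 20-45% against 60-90%, and single contrasts against baseline remain valid.

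The 3-fold variance ratio follows from the nesting at a constant rate. The power figures rest on assumed visit rates, an assumed effect pattern and patient risk that is constant over time. The likely harm is a missed effect in the mixed-model analysis of secondary outcomes 2-4. The primary SGRQ analysis, the sample size, the CACE analyses and the log-rank test are not affected.

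**What to change.** In the SAP's Statistical Analysis section, replace the cumulative totals with non-overlapping counts for 0-3, 3-6 and 6-9 months. Include an offset of log time alive and under observation in each interval. Fit a negative binomial mixed model, or use patient-clustered robust standard errors, so that interval-level overdispersion does not inflate type I error.

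Derive the 0-6 and 0-9 month rate ratios as ratios of summed interval means, by the delta method or standardization; they are not simple contrasts of the interval log rate ratios. Alternatively, fit each cumulative total in its own model with one row per patient and an offset.

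State in the same sentence whether the baseline count is a covariate or a row. Recoding does not change what the interaction gate asks: with post-baseline interval rows, a constant rate ratio of 0.7 still passes it in only about 5% of trials. That is a separate matter.

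The cost is SAP wording and a data step. The planned time-to-event analysis already needs dated visits and deaths, so no new data are required.
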